#### Screening Period (Day -28 to Day -3):

After signing the informed consent form (ICF), Screening assessments will be performed within 28 days of the planned first dose to ensure the eligibility of participants. Screening assessments will include:

- Medical and surgical history
- Demographic data
- Hepatitis/human immunodeficiency virus (HIV) serology
- Inclusion/Exclusion Criteria
- Weight and height
- Vein assessment
- Urine drugs of abuse (DOA) and alcohol/cotinine screen
- Physical examination (full)
- Laboratory safety tests (biochemistry, haematology, coagulation, urinalysis, urine microscopy and follicle-stimulating hormone (FSH) for post-menopausal female subjects only)
- 12-lead ECG
- Vital signs (supine systolic and diastolic blood pressure, pulse rate, and tympanic temperature)
- Adverse event (AE)
- SAE
- Prior and concomitant medication

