#### **10.7.4.1 Definitions**

#### **Adverse Events:**

An AE is any untoward medical occurrence in a patient or clinical trial subject administered an IMP, which does not necessarily have a causal relationship with this treatment.

It can therefore be any unfavourable and unintended sign (*i.e.* an abnormal laboratory finding), symptom, or disease temporally associated with the use of a medicinal product, whether or not considered related to the medicinal product.

Definition of an AE includes worsening (in severity and frequency) of pre-existing conditions ("Medical history") before first IMP administration and abnormalities of procedures (*i.e.* 12-lead ECG results) or abnormal laboratory results which are assessed as "clinically significant".

Final V3.0/ Date 07 December 2020

Confidential

Page 78 of 109

DNDi RD 777/34920 DNDi- 0690- 02

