#### Clinically Significant Laboratory Procedures/Abnormalities:

For every laboratory assessment, the Investigator will evaluate if the laboratory test result is normal or abnormal. If abnormal (after repeat test as required), the Investigator will assess if this finding is clinically significant or not. If a laboratory parameter is abnormal and clinically significant, it should be reported as an AE.

An abnormal laboratory/procedure result must be compared with the previous value taking into account normal values in the studied population/country.

A TEAE is a new event after the administration of the first dose of the study drug or a worsening in the condition. In the case of abnormal laboratory/procedure tests results, it is an increase in severity (clinical intensity) of the abnormality which is judged clinically significant by the Investigator.

Any abnormalities will be assessed as "clinically significant" (and therefore have to be reported as an AE) if they meet at least one of the following conditions:

- The abnormality suggests a disease and/or organ toxicity AND this abnormality was
  not present at the Screening visit or is assessed as having evolved since the
  Screening visit,
- The abnormality requires medical intervention or concomitant therapy,
- Furthermore, laboratory abnormalities associated with clinical signs and symptoms will also be considered clinically significant.

When reporting an abnormal laboratory result as an AE, a clinical diagnosis should be recorded rather than the abnormal value itself, if available. However, in these cases, the AE should be recorded as the syndromic clinical diagnosis (*i.e.* acute pancreatitis instead of each finding separately: high levels of amylase, high levels of lipase, abdominal pain and vomiting; "hypokalaemia" rather than "decreased potassium levels").

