#### 10.7.4.2 Adverse Events

## 10.7.4.2.1 Recording Adverse Events

AEs will be recorded from the time of providing written informed consent until discharge from the study at the follow-up visit.

Any untoward medical event which occurs after the completion of the clinical trial and is reported by the subject to Simbec-Orion will be classified as a "post-study event". All serious post study events assessed as related to the IMP will be reported to the pharmacovigilance of the Sponsor.

During each study visit the subject will be questioned directly regarding the occurrence of any adverse medical event according to the schedule in the source. All AEs, whether ascribed to study procedures or not, will be documented immediately in the source. This will include the date and time of onset, a description of the AE, severity, duration, actions taken, outcome and an Investigator's current opinion on the relationship between the study drug and the event. A diagnosis and final opinion on the relationship between the study drug and the event will be provided at the end of the study by the Investigator.

DNDi RD 777/34920 DNDi- 0690- 02

Final V3.0/ Date 07 December 2020

Confidential

Page 80 of 109

Any subject who withdraws from the study due to an AE will be followed up until the outcome is determined and written reports provided by the Investigator.

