# **Grading of Adverse Event Severity**

The Investigator will evaluate each event with regard to its severity. The severity of the AEs will be determined in the following manner:

- Mild: An AE that is easily tolerated by the subject, causes minimal discomfort, and does not interfere with everyday activities
- Moderate: An AE that is sufficiently discomforting to interfere with normal everyday activities; intervention may be needed
- Severe: An AE that prevents normal everyday activities; treatment or other intervention usually needed
- Life-Threatening: The subject is at significant risk of life; it does not refer to an event which hypothetically might have caused death if it were more severe (life threatening consequences, urgent intervention required).
- Death: Death related to an event.

When the severity of an AE changes over time, only one AE and the maximum severity will be recorded in the eCRF for each separate event. If the AE resolves but then recurs, each will be recorded as a separate AE, with the appropriate start and stop times.

To ensure no confusion or misunderstanding of the difference between the terms "serious" and "severe," which are not synonymous, the following note of clarification is provided:

The term "severe" is often used to describe the severity of a specific event (as in mild, moderate, or severe myocardial infarction); the event itself, however, may be of relatively minor medical significance (such as severe headache). This is not the same as "serious," which is based on patient/event outcome or action criteria usually associated with events that pose a threat to a patient's life or functioning. Seriousness (not severity) serves as a guide for defining regulatory reporting obligations.

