#### 10.9.2.5.3 Safety Data

All safety data will be listed, in addition:

**AEs:** All AEs will be coded using the Medical Dictionary for Regulatory Activities (MedDRA) dictionary (the most up to date version that is available at the time of database build will be used and will be listed in the DMP). The MedDRA dictionary will not be updated during the course of the study.

All AEs and SAEs, including those which occurred prior to the first dose of IMP, will be listed. Only TEAEs, *i.e.* existing conditions that worsen or events that occur during the course of the study after administration of IMP, will be included within the summary tables.

An overall summary of AEs will be produced including the number of TEAEs; the number and % of subjects reporting at least 1 TEAE, serious TEAE, TEAE leading to withdrawal from the study; the number and % of subjects reporting TEAEs by severity and relationship to IMP.

DNDi RD 777/34920 DNDi- 0690- 02

Final V3.0/ Date 07 December 2020

Confidential

Page 100 of 109

The number of TEAEs and the number and % of subjects reporting at least 1 TEAE will be tabulated by system organ class (SOC) and preferred term. A subject reporting multiple episodes of a particular AE within a treatment period will only contribute 1 count towards the corresponding SOC and preferred term.

The number of TEAEs and the number and % of subjects reporting at least 1 TEAE will be tabulated by preferred term and sorted by descending frequency on the total number of subjects with that AE. A subject reporting multiple episodes of a particular AE within a treatment period will only contribute 1 count towards the corresponding preferred term.

In addition, the number and % of subjects reporting TEAEs will be tabulated by maximum severity and strongest relationship to IMP. For the summary of TEAEs by severity, if a subject has multiple events occurring within the same SOC or preferred term the event with the highest severity will be counted. Similarly, for TEAEs by relationship to IMP, if a subject has multiple events occurring within the same SOC or preferred term, the event with the highest association to IMP will be counted.

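### For AEs that begin between consent and the first dose and are still ongoing at dosing, the one-record, maximum-severity rule does not capture the post-dose worsening that the TEAE definition counts

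*Protocol*

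**What the plan says.** Collection starts well before dosing. Section 10.7.4.2.1 states: "AEs will be recorded from the time of providing written informed consent until discharge from the study at the follow-up visit". The synopsis adds that "Screening assessments will be performed within 28 days of the planned first dose", and the flow charts schedule AE collection at Screening, Day -2 and Day -1.

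The recording rule is in section 10.7.4.2.2, under the grading of severity: "When the severity of an AE changes over time, only one AE and the maximum severity will be recorded in the eCRF". It applies per separate event. The only stated route to a second record is this: "If the AE resolves but then recurs, each will be recorded as a separate AE, with the appropriate start and stop times".

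The TEAE definition appears twice, and each time it has two limbs. Section 10.7.4.1 states: "A TEAE is a new event after the administration of the first dose of the study drug or a worsening in the condition". Section 10.9.2.5.3 describes TEAEs as "existing conditions that worsen or events that occur during the course of the study after administration of IMP" and restricts the AE summary tables to them. All AEs, including those before dosing, are listed.

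Section 10.9.2.1 makes the frequency and severity of TEAEs part of the primary endpoint.

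**The concern.** The definition needs to know whether a condition became worse after the first dose. The recording rule keeps one severity, the highest, without saying when it was reached. For an event that spans the first dose, that timing is exactly what decides whether it is a TEAE and at what severity it is tabulated.

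The gap arises at data capture. Under section 10.9.1 the SAP need only be agreed before database lock, and a derivation rule written then cannot recover a date that nobody was asked to record.

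Events spanning the first dose are conceivable here. Caffeine is stopped 3 days before dosing (section 10.5.3.4). Headache was among the most common TEAEs in the single-dose study (section 8.6.1). All Part C subjects receive iohexol on Day -1. These links are inference: the protocol does not say that they produce AEs that continue into dosing.

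**Working it through.** The protocol states no figure that depends on this point, so the check is mainly logical: which kinds of event can be classified from the information the protocol requires?

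**Inputs.** Collection window from section 10.7.4.2.1. Items recorded per AE from the same section: onset date and time, description, severity, duration, actions, outcome and relationship, with no date of severity change and no severity at first dose. Recording rule from section 10.7.4.2.2. TEAE definition from sections 10.7.4.1 and 10.9.2.5.3. Source location from Table 10, which places AEs in the eCRF. Allocation of 6 active and 3 placebo per cohort from section 10.1.

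**Step 1: apply the rules to each kind of event.**

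| Event | What is recorded | Can TEAE status be derived? |
|---|---|---|
| New event after first dose | Post-dose onset | Yes |
| Medical-history condition that worsens after dose | An AE in its own right under section 10.7.4.1, so it can have its own onset | Yes |
| Pre-dose AE that resolves and recurs after dose | Separate record with its own start | Yes |
| AE with onset between consent and first dose, ongoing at dosing, severity changes | One record: pre-dose onset, maximum severity | No |

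Only the fourth row fails.

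**Step 2: show the failure with two illustrative subjects.** Both have a headache starting on Day -1 and ending on the same later date.
- Subject 1: mild on Day -1, moderate on Day 2. This is worsening after dosing, so it is a moderate TEAE.
- Subject 2: moderate on Day -1, mild by Day 1. There is no worsening after dosing, so it is not a TEAE.

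Under the recording rule both have onset Day -1, the same duration and severity moderate. These fields do not separate them.

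**Step 3: direction of error.** If TEAE status follows onset date, both are excluded and Subject 1 is wrongly omitted. If every AE ongoing at first dose is counted, both are included and Subject 2 is wrongly added. The protocol does not choose between these rules, so the direction is not fixed.

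**Step 4: size per misclassified subject.** The shift in the proportion with at least one TEAE is 1/n, provided the subject has no other TEAE.
- One cohort, active: 1/6 = 16.7 percentage points.
- One cohort, placebo: 1/3 = 33.3 percentage points.
- Four Part A cohorts pooled, active: n = 4 × 6 = 24, and 1/24 = 4.2 points.
- Four Part A cohorts pooled, placebo: n = 4 × 3 = 12, and 1/12 = 8.3 points.

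These figures describe the effect of any single error in groups of this size. They say nothing about how often this one occurs.

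**The case against.** A reader might infer that the whole worsening limb cannot be derived. The protocol does not support that. Section 10.7.4.1 states: "Definition of an AE includes worsening (in severity and frequency) of pre-existing conditions", and it ties these to medical history. Such a condition can therefore have an AE record with a post-dose onset. Laboratory and ECG worsening rests on dated measurements.

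A reader might also infer that these events are lost from the primary endpoint tables. That does not follow either. Loss occurs only under an onset-date derivation, which the protocol does not prescribe, and the alternative over-counts. The events remain in the listings in any case.

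It can be argued that the one-record rule applies to each separate event, so that post-dose worsening could itself be treated as a separate event. This is a possible reading, but the only exception the rule names is recurrence after resolution. If worsening is meant to open a new record, the section needs to say so.

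Other recorded items, such as relationship to drug, actions taken and concomitant medication, could help to tell two cases apart. The eCRF, which is not shown, might also hold a further field. But relationship is a judgement and not part of the TEAE definition, and none of the items the protocol requires dates the change in severity.

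Two further points stand. Subjects are screened healthy volunteers whose eligibility is re-confirmed before each dose, so few such events are likely. And the stopping criteria in section 10.2.2 use seriousness, severity and relationship, not TEAE status, so the gap does not alter them.

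**Conclusion.** The point holds for one class of event: an AE with onset after consent and before the first IMP dose, still present at dosing, whose severity changes. For these, the recording rule in section 10.7.4.2.2 does not supply what the TEAE definition in sections 10.7.4.1 and 10.9.2.5.3 requires, and the SAP cannot restore it afterwards.

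The consequence is possible misclassification in either direction in the tables for a primary endpoint. The per-subject shifts worked out above apply only if that subject has no other TEAE, and the number of such subjects cannot be estimated from the protocol. The conclusion assumes that the eCRF collects what the protocol describes and no additional severity history. The practical effect is probably small, but the inconsistency is between a fixed recording rule and the definition of a primary endpoint, and it is easily removed.

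**What to change.** Reconcile section 10.7.4.2.2 with sections 10.7.4.1 and 10.9.2.5.3. Limit the single-record, maximum-severity rule to severity changes that fall on the same side of the first IMP dose. If an AE present before the first dose increases in severity after it, open a new AE record with the date and time of worsening and the new severity, and derive TEAE status from that onset.

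The cost is one sentence in the protocol, one line in the eCRF completion guideline and a few extra AE records. It needs no new assessments and does not touch clinical management.

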#### **Assessment of Causality**

For both serious and non-serious AEs, the Investigator is required to assess the possible relationship between the AE and each study drug (*i.e.* to determine whether there exists a reasonable possibility that the study drug caused or contributed to the AE).

This means that there are facts (evidence) or arguments to suggest a causal relationship.

To help investigators with the decision binary tree yes/no (i.e. Related/Not related) in the evaluation of causality, the Council for International Organizations of Medical Sciences

DNDi RD 777/34920 DNDi- 0690- 02

Final V3.0/ Date 07 December 2020

Confidential

Page 81 of 109

(CIOMS VI) group recommends that investigators be asked to consider the following before reaching a decision:

- Medical history (including presence of risk factors)
- Lack of efficacy/worsening of existing condition
- Study medications
- Other medications (concomitant or previous)
- Withdrawal of study medication, especially following trial discontinuation / end of study medication
- Erroneous treatment with study medication (or concomitant)
- Protocol related procedure

## The terms for reporting are:

- Definitely related. The AE and administration of study agent are related in time, and a direct association can be demonstrated.
- Probably related. The AE and administration of study agent are reasonably related in time, and the AE is more likely explained by study agent than other causes.
- Possibly related. The AE and administration of study agent are reasonably related in time, and the AE can be explained equally well by causes other than study agent.
- Probably not related. A potential relationship between study agent and the AE could exist (*i.e.* the possibility cannot be excluded), but the AE is most likely explained by causes other than the study agent.
- Not related. The AE is clearly explained by another cause not related to the study agent.

Note: When compared to Binary "regulatory" classification, "not related" corresponds to "not related, probably not related" and "related" corresponds to "possible, probable and definitely related".

#### **Adverse Event Seriousness Assessment**

The Investigator will evaluate the seriousness of any event as per the definition in Section 10.7.4.1.

#### 10.7.4.2.3 Analysis of Events by the Sponsor

The Sponsor will also evaluate the seriousness of all events which are reported to him by the Investigator, and the causality of the study drug and any other treatments for each AE.

AEs for which the Investigator consider that a causal link with the study product is a reasonable possibility will be considered to be suspected adverse effects. Should the evaluations of the Sponsor and the Investigator differ with regard to causality and the event being serious, then both will be reported in the declaration of suspected adverse reactions.

The Sponsor is responsible for determining the expectedness of the SAE, using the IMP reference safety information. Each SAE has to be classified by the Sponsor as expected or unexpected for the IMP.

Confidential

Page 82 of 109

DNDi RD 777/34920 DNDi- 0690- 02

Final V3.0/ Date 07 December 2020

# **10.7.4.2.4 Reporting Serious Adverse Events**

The Investigator is required to notify the study sponsor and pharmacovigilance provider if appropriate within 24 h of becoming aware of the occurrence of an SAE. A copy of the written report of the event should promptly be sent to the study Sponsor for information purposes, in accordance with International Council for Harmonisation of Technical Requirements for Registration of Pharmaceuticals for Human Use (ICH) guidelines.

The Investigator will notify the Sponsor without delay on the day of discovery of any SAEs.

# The Investigator must:

- note in the participant's medical file the date on which he/she become aware of the SAE (at a follow-up visit or a telephone contact with the participant or a third person, etc);
- immediately inform (within 24 h of awareness of SAE by the Investigator) by telephone, the Sponsor Medical responsible, and the Sponsor Clinical Project Manager, and confirmed by an email to **[contact]** (**copy SAE\[contact]**)
- complete the SAE form and send it by email to [contact] (copy SAE\[contact]), immediately after of being informed of this event, without waiting for the results of the clinical outcome or of additional investigations, and in any case within 24 h of knowledge by the Investigator; this form includes a description of the event, onset date and seriousness criteria, duration, severity, causal relationship to study drug, outcome, measures taken and all other relevant clinical and laboratory data;
- provide the persons designated above, as they become available, additional information (follow-up SAE form) with all relevant information that could contribute to the clarification of the SAE and to the assessment of potential risk for the study subjects and with anonymised copies of the documents which provide additional useful information, such as hospital admission reports, reports of further consultations, laboratory test reports, reports of other examinations aiding diagnosis (where possible, the results from pre-treatment assessments should be appended for comparison with the results obtained under treatment), or the autopsy report, if autopsy is performed; any follow-up reports should be submitted as soon as possible, and if possible within 2 working days of knowledge, inform the persons designated above of the outcome, if not previously reported, and other relevant follow up information of the SAE as soon as possible;

The Investigator must also report all SAEs in the source by filling in the AE form. Where the same data are collected in the source and in the SAE form, the two forms must be completed in a consistent manner, and the same medical terminology should be used.

If the SAE is the reason of subject drop-out from the study, the Investigator will detail the reason for such a statement in the comment section of the form and the Sponsor Medical Responsible and Sponsor Clinical Project Manager will be informed immediately (within 24 h of the Investigator becoming aware of the event) by telephone and email.

The minimum criteria to be reported are as follows:

DNDi RD 777/34920 DNDi- 0690- 02

Final V3.0/ Date 07 December 2020

Confidential

Page 83 of 109

- a suspected IMP,
- an identifiable subject (at least study subject identification code number but no subject initials).
- an AE assessed as serious,
- an identifiable reporting source.

The outcome of the SAE shall be classified as following:

- recovered/resolved,
- recovering/resolving,
- recovered/resolved with sequelae,
- not recovered/not resolved,
- fatal,
- unknown.

Details should be given for the latter four categories.

• Start date of SAE or date when the AE becomes serious. SAE end date is the date of AE recovery.

